9 TREATMENT EVALUATION

9.1 Pre-treatment evaluation

- 9.1.1 A complete history and physical examination by a medical, radiation or surgical (ENT or Head and Neck Surgery) oncologist, and baseline laboratory studies, including complete blood count (CBC), complete metabolic panel (CMP) and fasting glucose or non-fasting HgbA1c will be performed within 30 days of starting metformin escalation. Negative pregnancy test is required 10-14 days before registration for women of child bearing age who maintain reproductive potential (i.e. have not undergone hysterectomy).
- 9.1.2 Sample collection for baseline correlative studies will be performed before initiation of metformin escalation as outlined in the study calendar.
- 9.1.3 One of the following combinations of imaging is required within 8-12 weeks prior to registration:

- a) A CT scan of the neck (with contrast) and a chest CT scan (with or without contrast), or
- b) A CT scan of neck (with contrast) and a PET/CT of neck and chest (with or without contrast). **Note:** A CT scan of neck and/or PET/CT performed for radiation planning and read by a radiologist may serve as both staging and planning tools.

Staging (T, N, M) will be performed by the treatment team following diagnosis and discussion at multi-disciplinary tumor conference, per standard of care practice. For the purpose of the study, the clinical TNM staging for each patient will be obtained by the PI or clinical coordinator from the medical record and entered into the study prior to treatment initiation.

9.1.4 Evaluation by a nutritionist and/or swallowing therapist is highly recommended within 2-4 weeks prior to the start of chemo-radiation treatment and should include evaluation for placement of prophylactic gastrostomy or other type of feeding tube. The decision to place a feeding tube should be individualized and may consider a number of factors including: prior weight loss, current nutritional status, size and location of the primary tumor (impacting high dose target volume), availability of feeding tube placement services, availability of speech and swallowing specialists, and social support. Feeding tubes may be placed after start of treatment at the discretion of the clinical team. If a tube is placed, documentation will be provided in the patient's protocol file if the tube was placed prophylactically (as a preventative measure) or therapeutically (because of nutritional compromise or other clinical indications).

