9.3 Evaluation following treatment

9.3.1 A brief history and physical examination by a medical, radiation or surgical (ENT or Head and Neck Surgery) oncologist, including laryngopharyngoscopy (mirror and/or fiberoptic and/or direct procedure), should be done at 10 weeks following completion of radiation then every 3 months through year 1 and every 4 months through year 2. A 30 day visit or telephone interview is required for evaluation of Adverse Events. Radiographic imaging (CT, MRI, or PET as appropriate) at these time points is highly recommended if disease progression is suspected by the treating physician. If performed, radiographic imaging to evaluate the patient for both local-regional recurrence and distant metastases is highly recommended.

- 9.3.2 Chest imaging: A chest CT or a PET/CT of chest is recommended once per year.
- 9.3.3 Biopsy of any lesion(s) suspicious for tumor recurrence is recommended as clinically indicated.
- 9.3.4 The initial post-radiation imaging evaluation (CT at 8-10weeks or PET-CT at 10-12weeks) after the completion of chemoradiation is recommended to assess disease response. The imaging can be contrast enhanced CT (neck and chest) or PET-CT of the head and neck or “whole body” PET/CT (minimum neck and chest) based on the preference of the treating clinician, but must be consistent with the pre-treatment imaging modality.

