12.1 Antitumor Effect – Solid Tumors

For the purposes of this study, patients should be reevaluated for response following completion of treatment as per current institutional protocol for this disease site: 1) spiral contrast enhanced computed tomography (CECT) at 8-10 weeks following completion of treatment or 2) positron emission tomography (PET) at 10-12 weeks following completion of treatment. No additional imaging or tests will be performed as part of the current protocol. Following the first post treatment scan, patients will continue routine surveillance using CECT or PET per institutional protocols.

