12.1.4.2 Evaluation of Non-Target Lesions

Complete Response (CR): Disappearance of all non-target lesions and normalization of tumor marker level Note: If tumor markers are initially above the upper normal limit, they must normalize for a patient to be considered in complete clinical response.

Incomplete Response/Stable Disease (SD): Persistence of one or more non-target lesion(s) and/or maintenance of tumor marker level above the normal limits

Progressive Disease (PD): Appearance of one or more new lesions and/or unequivocal progression of existing non-target lesions.

Although a clear progression of “non-target” lesions only is exceptional, the opinion of the treating physician should prevail in such circumstances, and the progression status should be confirmed at a later time by the review panel (or Principal Investigator).

12.1.4.3 Overall Response: overall response will be ascertained via clinical exam and imaging at 8-12 weeks post treatment completion according to the table below.

Target Lesions	Non-Target Lesions	New Lesions	Overall Response (measured at 8-12wk post treatment)
CR	CR	No	CR
CR	Non-CR/Non-PD	No	PR
PR	Non-PD	No	PR
SD	Non-PD	No	SD
PD	Any	Yes or No	PD
Any	PD*	Yes or No	PD
Any	Any	Yes	PD

* In exceptional circumstances, unequivocal progression in non-target lesions may be accepted as disease progression.

Note: Patients with a global deterioration of health status requiring discontinuation of treatment without objective evidence of disease progression at that time should be reported as “*symptomatic deterioration*”. Every effort should be made to document the objective progression even after discontinuation of treatment.

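### The response scan may be a PET-CT limited to the head and neck, so in patients with a PET/CT baseline a new chest lesion can be missed and the patient scored as a responder

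*Combined protocol and SAP*

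**What the plan says.** **Baseline (9.1.3).** Two imaging combinations are accepted, and both include the chest: "A CT scan of the neck (with contrast) and a chest CT scan (with or without contrast), or" "A CT scan of neck (with contrast) and a PET/CT of neck and chest (with or without contrast").

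**Response scan (9.3.4).** The menu is "The imaging can be contrast enhanced CT (neck and chest) or PET-CT of the head and neck" or a whole-body "PET/CT (minimum neck and chest) based on the preference of the treating clinician, but must be consistent with the pre-treatment imaging modality". Two of the three options state chest coverage. The head-and-neck PET-CT does not.

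**Scoring (12.1.4.2 and 12.1.4.3).** Progression of non-target disease is defined as "Appearance of one or more new lesions and/or unequivocal progression of existing non-target lesions". The overall response table gives CR or PR only when there are no new lesions, and PD whenever there is one. Section 13.2 counts CR or PR as a response, read at 8-12 weeks after treatment.

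**Other chest imaging.** Section 9.3.2 says "A chest CT or a PET/CT of chest is recommended once per year". Section 9.3.1 adds "If performed, radiographic imaging to evaluate the patient for both local-regional recurrence and distant metastases is highly recommended". Section 12.1 allows CT or PET for the response assessment, does not state PET coverage, and says "No additional imaging or tests will be performed as part of the current protocol".

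**The concern.** A finding of no new lesions cannot be made for a region that was not imaged. On two of the listed scans, a patient whose neck disease has responded but who has a new lung lesion is PD. On the third, the same patient can be CR or PR. Within the modality used at baseline, the choice is left to the treating clinician.

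The misclassification runs one way. A missed lesion turns a non-responder into a responder and never the reverse. The trial is single-arm and is judged against a fixed 40% rate, so no concurrent control group shares the error. One patient in 28 is 3.6 percentage points (1/28), enough to turn 16 responses into the 17 required. A missed lesion could also date a progression-free survival event late.

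**Working it through.** **1. Is chest imaging required at 8-12 weeks anywhere else?**

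| Place | What it governs | Closes the gap? |
|---|---|---|
| 9.3.4, consistency clause | Modality (CT or PET-CT) | In part: see step 2 |
| 12.1.3, same-method rule | Lesions already identified | No: it does not govern the search for new ones |
| 9.3.2 | Yearly chest scan, recommended | No: not tied to the response window |
| 9.3.1 | Imaging for distant metastases, recommended if imaging is done | No: not required |
| 9.2 Study Calendar | Timing of imaging | No: body coverage not stated |
| 12.1.7 Response Review | Blinded re-reading | No: only acquired images can be read |

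**2. Who is exposed?** A patient whose baseline was CT of neck plus chest CT must, under the modality clause, have CT at response, and that option covers neck and chest. Only patients whose baseline included PET/CT can have the limited PET-CT. They may also have one of the fuller scans.

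**3. The plan's own figures.** Inputs from 13.2: 40% against 60%, one-sided alpha 0.10, power 80%, n = 28, success at 17 or more.
- Normal approximation: n = [(1.2816 + 0.8416) × √0.24 / 0.20]² = 27.05, rounded up to 28. Power at 28 is 0.810, so the sample size and power reproduce.
- Exact binomial for 17 or more of 28: 0.0215 at a 40% rate and 0.551 at 60%. The cut-off is thus stricter than alpha 0.10 requires. That is a separate matter, but it is the baseline for what follows.

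**4. Size of the error, by assumption.** Let d be the share of locoregional responders with a new chest lesion and s the share of patients given the limited scan. The documents give neither. Assume d = 5% (range 3-10%), and that d does not depend on which scan is used.
- Locoregional response rate that yields a true 40%: L = 0.40/(1 − d) = 0.4211 at d = 5%.
- False responders as a share of all patients: f = s × d × L.
- Measured rate: 0.40 + f.
- Chance of at least one false responder: 1 − (1 − f)^28.

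Example with s = 0.5 and d = 5%: f = 0.5 × 0.05 × 0.4211 = 0.0105. The measured rate is 0.4105, and the chance of at least one false responder is 1 − 0.9895^28 = 0.26.

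| s | d | Measured rate | P(≥17 of 28) | At least one false responder |
|---|---|---|---|---|
| 0 | any | 40.0% | 0.0215 | 0 |
| 0.5 | 3% | 40.6% | 0.0253 | 0.16 |
| 0.5 | 5% | 41.1% | 0.0282 | 0.26 |
| 0.5 | 10% | 42.2% | 0.0376 | 0.47 |
| 1 | 3% | 41.2% | 0.0295 | 0.29 |
| 1 | 5% | 42.1% | 0.0365 | 0.45 |
| 1 | 10% | 44.4% | 0.0619 | 0.72 |

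The rows with s = 1 are upper bounds for each d, reached only if every patient has the limited scan.

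**5. Delay to a PFS event.** The calendar marks imaging every 3 months in year 1. If the next of those scans covers the chest, the delay is about 3 months. If the lesion is first seen at a chest scan one year after treatment, the delay is about 52 − 12 = 40 weeks.

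**The case against.** The strongest reply is that the gap is narrow. The modality clause keeps patients with a CT-only baseline on CT of neck and chest. Misclassification then needs three things together: a limited PET-CT, new chest disease by 8-12 weeks, and a locoregional response. This stands, and it is why the rows with s = 1 are bounds and not expectations. It does not close the gap. A head-and-neck PET-CT after a neck-and-chest PET/CT is the same modality, and 9.3.4 names it as acceptable.

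A reader might go further and infer any of three things that the documents do not support.

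- **That the false-positive rate breaches its planned level.** It does not: even the 6.2% bound is below 0.10. That margin comes from the strict cut-off of 17. A cut-off of 15 already has an exact error of 0.1025 with no misclassification.
- **That distant progression is routinely dated about 40 weeks late.** This overlooks the calendar imaging every 3 months in year 1, its footnote C on imaging at regular intervals, and the continuing surveillance described in 12.1. None of these guarantees chest coverage, so some delay is possible, but 40 weeks is the long end.
- **That the comparison with 40% is biased by exactly the amounts above.** This would require the benchmark to come from imaging that included the chest, which the documents do not say.

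**Conclusion.** The gap is real and confined to patients whose baseline included PET/CT. For them, the plan as written allows a scan that cannot support a finding of no new lesions in the chest, and the resulting error can only raise the response rate. At d = 5% with half of patients given the limited scan, the effect is about one percentage point on the response rate and a rise from 2.2% to 2.8% in the chance of a false positive. The bound at d = 10% with all patients so scanned is 44.4% and 6.2%. These figures rest on assumed values of d and s. The direction of the error and the existence of the gap do not. The effect is modest, but it falls on the primary endpoint, one patient can decide the result at the threshold, and the correction is cheap.

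**What to change.** In 9.3.4, state that whichever response scan is used must cover at least neck and chest, as at baseline, and remove or reword the head-and-neck PET-CT option. Repeat the coverage rule in 12.1, where PET coverage is not stated.

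Do not automatically class patients already scanned without chest coverage as failures. Recording them as unknown under 13.5.2 would count them as treatment failures. At d = 5%, 19 of every 20 locoregional responders so reclassified would be true responders, so a small upward bias would give way to a larger downward one. Report how many such patients there are, and give the response rate with and without them as a sensitivity analysis.

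The cost is one sentence in each of two sections and no new procedure, since two of the three listed scans already comply. The downsides are a longer scan field for some patients and a possibly slightly lower observed response rate.

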9.2 Study Calendar

	Pre-study	wk -2 (d3+/-2d)	wk 1 (d3+/-2d)	wk 2 (d3+/-2d)	wk 3 (d3+/-2d)	wk 4 (d3+/-2d)	wk 5 (d3+/-2d)	wk 6 (d3+/-2d)	wk 7 (d3+/-2d)	30 days post radiation completion	Post-study (wk17+/-2wk)	Post-study (yr1 Q3mos)	Post-study (yr2 Q4mos)
Metformin tx		<-----BID metformin----->											
Chemo-radiation tx			<-----XRT (Daily); chemotherapy (weekly)----->										
Collected information (ONCORE)													
Metformin pill diary/compliance form		x	x	x	x	x	x	x	x				
Eligibility checklist	x												
Informed consent	x												
T, N, M staging	x												
Demographics	x												
Physical Exam	x	x	x	x	x	x	x	x	x		x	x	x
Medical history	x												
Vital signs	x										x	x	x
Weight	x	x	x	x	x	x	x	x	x		x	x	x
Performance status	x	x	x	x	x	x	x	x	x		x	x	x
Adverse event evaluation		x	x	x	x	x	x	x	x	x	x		
CMP	x												
CBC, BMP	x	x	x	x	x	x	x	x	x		x	x	x
Glucose monitoring (if applicable) (A)		x	x	x	x	x	x	x	x				
Disease response/radiologic evaluation											x	x	x
Pregnancy test	x (B)												
Imaging (C)	x										x	x	x
Laryngopharyngoscopy											x	x	x
pre-study items to be collected within 30 days of initiation of metformin treatment													
Pill diary/compliant may be discussed or completed via telephone.													
A: patients with hypoglycemia (<=60mg/dl) will receive instructions and supplies for BID glucose monitoring and recording													
B: Serum or urine pregnancy test (women of childbearing potential).													
C: Required within 8-12 weeks prior to registration, at end of radiation treatment, and at regular intervals following treatment completion.													
D= day, Wk= week, Mos= months, Yr= year; d3+/-2d= to be completed on day 3 of any given week, +/- 2days													

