7.2.1 Hypoglycemia: Although the risk of hypoglycemia in euglycemic patients receiving metformin is very low, patients in this trial might have a low caloric intake due to complications of treatment, and will undergo weekly blood glucose monitoring.

If based on these lab values or associated symptoms, the treating physician diagnoses hypoglycemia (Grade 1 or greater), study drug treatment will be halted, while concurrent chemoradiation will continue. Once blood glucose normalizes, metformin will be restarted and the dose should be decreased to the next available lower dose (see table below) with daily monitoring of blood glucose. Patients will

be provided equipment and supplies for twice daily blood glucose checks, along with a form used to record values.

Instructions for Metformin Dose Reductions due to Adverse Events	
Starting Dose (mg PO BID)	Reduced Dose (mg PO BID)
1500 mg	1350 mg
1350 mg	1000 mg
1000 mg	850 mg
850 mg	500 mg
500 mg	0 (off treatment)

If hypoglycemia resolves to < Grade 1 after 7 days, daily monitoring will be discontinued and the patient will resume the previous dose. All dose de-escalation and re-escalation will be recorded in source documentation. If **hypoglycemia** symptoms persist **for more than 7 days**, the study drug will be stopped and this will be considered a DLT.

722 Gastrointestinal toxicity: In the event of grade 2-4 gastrointestinal toxicity (typically involving flatulence or diarrhea), patients will be supported with loperamide, at dosing schedules recommended in the package insert. Gastrointestinal side effects typically subside within 4-6 weeks of initiating metformin treatment.

Efforts should be made to maintain the dose as close to the planned total daily treatment dose as much as possible. Before dose-reducing, alterations to the daily intake schedule of metformin should be taken to reduce gastrointestinal symptoms, including taking metformin with food rather than before meals.

If alterations in intake schedule are insufficient in reducing gastrointestinal toxicity to \leq grade 1, the metformin dose should be decreased to the next available lower dose for 1 week with loperamide support until symptoms subside.

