13.0 STATISTICAL CONSIDERATIONS

13.1 Study Design/Endpoints

This is a single arm combination Phase I/II trial of Metformin to determine the maximum tolerated dose (MTD) of metformin among 2 dose levels (850mg, 1500mg administered orally, twice daily) and to evaluate the disease response rate at the MTD. Standard of care conventional chemotherapy (cisplatin) will be administered using current clinical protocols. Dose-limiting toxicity will be ascertained using the Common Terminology Criteria for Adverse Events v4.0. The dose-limiting toxicities ascertained for the phase I component will be gastrointestinal toxicity and hypoglycemia requiring dose reduction. The primary outcome for the phase II component will be disease response rate (RECIST criteria) at 8-12 weeks post treatment completion.

The secondary outcomes will be disease free and overall survival. All analysis of secondary studies will be performed post hoc and will not be used to influence clinical decision making during the therapeutic trial.

This study began as a Phase I “3+3”/ Phase II “Simon” design, but was converted into Bayesian Optimal Interval (BOIN) design before completion of the Phase I to provide monitoring of toxicity beyond the Phase I cohort. BOIN design has algorithmic escalation/de-escalation rules easy to implement like a traditional 3+3 design but allows for specification of the target DLT rate, different size cohorts, is more likely to correctly select the MTD and allocate more patients to the MTD and expands consistent toxicity monitoring to the entire cohort. BOIN design with a target DLT rate of 0.3 and cohort size of 3 begins exactly in the same fashion as the “3+3” allowing for the implemented design change in early stages. Calculations were done using R package BOIN.³²

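### The trigger for home glucose monitoring is stated three different ways in section 7.2.1, the study calendar and the patient's glucose form

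*Combined protocol and SAP*

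**What the plan says.** Four places deal with hypoglycemia that leads to monitoring.

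- **Section 7.2.1 (metformin dose modifications).** "If based on these lab values or associated symptoms, the treating physician diagnoses hypoglycemia (Grade 1 or greater), study drug treatment will be halted", while chemoradiation continues. Then: "Once blood glucose normalizes, metformin will be restarted and the dose should be decreased to the next available lower dose", with glucose monitored daily. The next sentence says patients will "be provided equipment and supplies for twice daily blood glucose checks" and a form for recording the values. No mg/dl threshold is given.
- **Section 11 (toxicities).** It repeats the diagnosis from lab values or symptoms, with daily monitoring after restart. It gives neither a grade nor a threshold.
- **9.2 Study Calendar.** The glucose-monitoring row is marked as applying only where applicable and refers to note A: "patients with hypoglycemia (<=60mg/dl) will receive instructions and supplies for BID glucose monitoring and recording". Note A has no symptom route and no grade.
- **Blood glucose monitoring form (the second appendix labelled B).** It tells the participant that home monitoring will be asked for when blood glucose is high.

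Two further statements concern the DLT. Section 13.1 says: "The dose-limiting toxicities ascertained for the phase I component will be gastrointestinal toxicity and hypoglycemia requiring dose reduction". Section 7.2.1 says that if hypoglycemia symptoms last more than 7 days, "the study drug will be stopped and this will be considered a DLT".

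**The concern.** Under 7.2.1, home checks accompany the restart of metformin at a lower dose. Both 7.2.1 and section 11 note that these patients may be eating little because of their treatment. If the passages name different patients, who is monitored depends on which page the site has open. The calendar is the natural working page for coordinators, and its glucose row points only to note A. A patient diagnosed on symptoms, or at a reading above 60 mg/dl, has metformin halted and then reduced under 7.2.1, yet is not described by note A. A patient with low glucose who reads the form is told that it is meant for the opposite problem.

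The home readings also bear on a later decision. Section 7.2.1 ends the monitoring and returns the patient to the previous dose if hypoglycemia has fallen below Grade 1 after 7 days. Without daily readings, that judgement has less to rest on.

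**Working it through.** The trigger is a question of wording, so the check sets the passages side by side.

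**Step 1. Triggers as written**

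| Place | Basis | Symptom route | Grade | Glucose threshold |
|---|---|---|---|---|
| 7.2.1 | Physician diagnosis | Yes | 1 or greater | None |
| Section 11 | Physician diagnosis | Yes | None | None |
| Calendar note A | Lab reading | No | None | <=60 mg/dl |
| Glucose form | Reading described as high | No | None | None |

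**Step 2. Apply them to three patients**

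| Patient | Home checks under 7.2.1 | Covered by note A | Covered by the form's wording |
|---|---|---|---|
| Physician diagnoses hypoglycemia; glucose <=60 mg/dl | Yes | Yes | No |
| Physician diagnoses hypoglycemia on symptoms, or on a reading above 60 mg/dl | Yes | No | No |
| High glucose, no hypoglycemia | No | No | Yes |

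The second row separates 7.2.1 from note A. The form's wording matches neither passage in any row where monitoring is called for.

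**Step 3. Does note A reach the DLT count?** Section 13.1 counts hypoglycemia that requires a dose reduction and grades it by a named scale: "Dose-limiting toxicity will be ascertained using the Common Terminology Criteria for Adverse Events v4.0". It mentions neither 60 mg/dl nor the calendar. The halt and the reduction are set in 7.2.1 (and section 11), not in note A. Note A decides only who receives supplies, so reading it in place of 7.2.1 does not directly change the count.

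**Step 4. The separate conflict that does reach the count.** Under 7.2.1 every diagnosed event leads to a lower dose at restart. Take a patient whose symptoms clear within the week:

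- Under 13.1 the dose was reduced for hypoglycemia, so this is a DLT.
- Under 7.2.1 symptoms did not last more than 7 days, so this is not a DLT.

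Section 13.2 de-escalates at an observed rate of 0.3585 or more and escalates at 0.2365 or less. With 3 patients, 1/3 = 0.333 lies between the limits (stay), and 2/3 = 0.667 exceeds 0.3585 (de-escalate). With 6 patients, 2/6 = 0.333 is stay and 3/6 = 0.500 is de-escalate. These agree with the table in 13.2. One event classified differently can therefore change the recommendation at either point.

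**The case against.** **The example depends on a scale the documents do not reproduce.** The 7.2.1 trigger is qualified by grade, and the documents do not give the CTCAE glucose range for Grade 1. Whether a symptomatic patient above 60 mg/dl would be graded at all cannot be settled from them, and the reference to glucose normalizing presumes an abnormal value. This stands as a limit: the size of the gap between Grade 1 and 60 mg/dl is unknown. But nothing in the documents shows that the two criteria coincide, and only one has a symptom route. The conflict with the form needs no scale at all.

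**Note A does not exclude anyone.** It does not say that only these patients receive supplies, and a site that follows 7.2.1 complies with both passages. That is fair, and it would be too strong to say patients are denied monitoring. The risk is omission by staff who follow the calendar row, which refers to nothing else.

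**Patients are seen weekly anyway.** Weekly visits and weekly blood tests continue for everyone, and metformin restarts only after glucose normalizes. This lowers the stakes, but weekly tests do not supply the daily monitoring that 7.2.1 asks for after restart.

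**Stronger readings that a reader might infer, and that the documents do not support:**

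- *Note A changes the number of DLTs.* It sets no halt, reduction or DLT. At most, missing home readings could make persistence beyond 7 days harder to judge.
- *A broad trigger would drive the trial across its toxicity boundaries.* That needs high assumed rates of hypoglycemia. Sections 7.2.1 and 11 call the risk very low, and 13.2 expects a DLT rate from all causes below 10% even at the highest dose.
- *Daily and twice-daily monitoring contradict each other.* They sit in consecutive sentences of 7.2.1 and read naturally as two checks on each day; note A and the form also say twice a day.
- *The stopping rules conflict.* Section 7.2.1, section 11 and the form all use about one week, and no patient is shown to be handled differently.

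**Conclusion.** The inconsistency is real and minor. Section 7.2.1, calendar note A and the patient's form state three different triggers for the same home monitoring, and section 11 states the diagnosis without a grade or threshold. The practical consequence is that monitoring required by 7.2.1 could be missed for a patient restarted on metformin after a diagnosis made on symptoms or at a reading above 60 mg/dl. This assumes that such diagnoses occur and that some staff work from the calendar. The documents give no rate for either, so no number of affected patients is offered.

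The DLT count is not affected by note A. It is affected by the separate disagreement between 13.1 and 7.2.1 over whether a dose reduction alone, or only symptoms lasting more than 7 days, makes hypoglycemia dose-limiting. If the count is addressed, it should be addressed on that ground.

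**What to change.** State one trigger for home glucose monitoring and use the same wording in section 7.2.1, section 11, calendar note A and the blood glucose monitoring form. The trigger is for the sponsor's clinicians to choose; the statistical request is only that the four places agree. Have note A refer to 7.2.1 so that the calendar cannot drift from it again.

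Separately, reconcile 13.1 with 7.2.1 so that one statement says when hypoglycemia is a DLT, and have the table in 13.2 count events under that statement.

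The cost is wording in four places for the trigger, plus 13.1 and the DLT sentence of 7.2.1 for the count, and a reissued patient form. If the broader trigger is kept, a few more home kits may be needed. Sample size, visit schedule and analysis do not change.
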